#### 5.6.1.1 *Pharmacokinetic concentrations*

Individual values will be listed chronologically for each serum concentration. Concentrations below the lower limit of quantification (LLOQ) will be treated as LLOQ/2 for summary statistics and graphs and reported as <LLOQ in data listings. Any missing concentration data will not be imputed.

Concentrations will be summarized by planned time point using both arithmetic and geometric means, standard deviations, coefficient of variations expressed as percentages (CV%), medians, minimums, and maximums.

GEN3014 concentration data will be presented graphically by actual time point, using individual curves of concentrations. All available data will be shown on these figures.

#### 5.6.1.2 *Pharmacokinetic parameters*

Based on the availability of the data and quantifiable concentrations of GEN3014 (or daratumumab SC in Expansion Part B) available [Table 9](#) lists the PK parameters to be derived for each subject. All pharmacokinetic parameters will be listed by subject and summarized by cycle and cohort.

**Table 9: PK parameters**

AUC 0-last	Area under the plasma concentration-time curve, from time zero to the last quantifiable concentration (mass x time x volume  )
AUC inf	Area under the plasma concentration time curve from time zero to infinity (mass x time x volume  )
C max	Maximum observed drug concentration in plasma after each administration (mass x volume  )
t max	Time of maximum observed concentration (time)
t 1/2	The elimination half-life associated with the terminal slope of a semi logarithmic concentration-time curve (time)

CL	Apparent total plasma clearance (volume x time  )
C trough	Observed pre-dose drug concentration

Additional parameters such as dose normalized Cmax and AUCs, apparent volume of distribution, accumulation ratios may be calculated to fully characterize the PK profiles of GEN3014.

All subjects in the PAS 1 for which PK parameters can be calculated will be included in the summaries. Descriptive statistics provided will include the number of subjects, arithmetic mean, standard deviation (SD), arithmetic coefficient of variation, reported as a percentage (CV%), median, minimum, and maximum. Geometric mean and geometric CV% will be calculated for continuous PK parameters. Tmax will be presented as median, minimum, and maximum.

Dose-response between dose and PK parameters will be presented. Associations between PK parameters and covariates such as weight, age, as well as relationships between emerging observations of safety, efficacy or pharmacodynamic biomarkers and plasma exposure may be explored graphically by the sponsor, possibly outside the scope of this SAP depending on the findings.

If deemed applicable, compartmental modelling approaches may be performed by the sponsor outside of the scope of this SAP.

### **5.6.2 Pharmacodynamics**

Pharmacodynamic summaries will be presented based on the BAS.

#### **5.6.2.1 Cytokine, chemokine and immunophenotyping measures**

Cytokine and immunophenotyping measures will be summarized in descriptive tables by time point, using mean, geometric mean, median, minimum, maximum, n, standard deviation, and geometric coefficient of variation (CV%).

Cytokine and immunophenotyping measures will also be graphed using median and standard error (SE) over time (by visit), where each line represents one cohort. Each cohort will be indicated with a different colour.

#### **Cytokine and chemokines**

The primary set of cytokines include IL-2, IL-6, IL-8, IL-10, IFN $\gamma$  and TNF $\alpha$ . Cytokine data below LLOQ (if determined for the assay) will be handled as (LLOQ)/2 in summary statistics and reported as is in data listings.

A graphical overview of all cytokines in Cycle 1 data will be provided.

#### **Immunophenotyping and complement analysis**

The immunophenotyping parameters are

- T-cells: CD3+, CD3+CD4+, CD3+CD8+
- NK-cells: CD3-CD56+/CD16+,
- B-cells: CD3-CD19+,
- monocytes: CD14+,
- complement analysis parameters: C2 and CH50.

The baseline value of the parameter will be presented by cohort, as well as the maximum absolute change and maximum absolute percentage change. For T-cells the maximum increase/expansion (and maximum percentage increase/expansion) from baseline will be presented. For NK-cells, B-cells, monocytes and complement analysis parameters, the maximum decrease/depletion (and maximum percentage decrease/depletion) will be presented.

Absolute and percentage changes from baseline in Cycle 1 will be presented in figures.

5.6.2.2

CCI

CCI

### 5.6.3 *Immunogenicity*

At sample level, the presence or absence of any anti-drug antibodies to GEN3014 or rHuPH20 (for subjects treated with daratumumab SC in Expansion Part B), will be listed by subject and visit. Summaries of positive anti-drug antibodies will be presented by visit. The number and percent of subjects with anti-drug antibodies will be summarized overall and by time point, using the Immunogenicity Analysis Set (IAS).

By using the *by subject and visit ADA status*, the *subject level ADA status* is defined as positive if

- Negative at baseline and at least one positive post-baseline result, or
- Positive at baseline and at least one positive post-baseline result with a titer at least 2-fold higher than baseline

subjects with no post-baseline ADA assessment will have a missing ADA status.

If assessed, neutralizing antibodies will be summarized (positive/negative).

Associations between ADA status (positive/negative, titer levels) and PK (AUC,  $C_{trough}$ ), major safety signals and efficacy will be explored, if possible.

#### **5.6.4 Rate of MRD Negativity and Duration of MRD Negativity**

Minimal residual disease (MRD) negativity is defined as no malignant clone sequence being detected at a given threshold in PBMCs or ctDNA (e.g. for  $10^{-5}$ , the clone sequence is not detected in the background of 100,000 nucleated cells). For evaluation of MRD negativity rate, subjects are considered MRD negative if there is at least one on-treatment MRD negative whole blood sample; all remaining subjects in the analysis set are considered MRD positive (e.g. those who only have MRD positive test results or those who have no MRD assessment data). Duration of MRD negativity is defined as the number of days from the first documentation of MRD- to the date of MRD status change (not MRD-). The primary MRD- threshold is selected as of  $10^{-5}$ . Other thresholds, including  $10^{-4}$  and  $10^{-6}$ , may also be explored.

MRD- rate analyses will be performed in a similar manner as for ORR, and duration of MRD- analyses will be conducted in similar methods for DOR.

PFS and OS analysis by MRD negativity status may be performed to assess the relationship between MRD negativity status and PFS/OS as part of exploratory analyses.

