ADA=anti-drug antibody; C=cycle; D/d=day; DNA=deoxyribonucleic acid; h=hour(s); IHC=immunohistochemistry; min=minutes; PBMCs=peripheral blood mononuclear cells; PK=pharmacokinetic(s); RNA=ribonucleic acid; R/R AML=relapsed or refractory acute myeloid leukemia; R/R DLBCL=relapsed or refractory diffuse large B-cell lymphoma; RRMM=relapsed or refractory multiple myeloma; seq=sequencing; UNS=unscheduled.

1. After flush.
2. ADA and biomarker samples in even cycles only.
3. Cycle 2 only.
4. For R/R DLBCL: collect sample at C3D1 only.
5. For R/R AML: collect samples at C2D1 and C3D1. For RRMM: collect sample at C4D1 only. Testing at these time points is for immunophenotyping only.
6. Collect if clinically feasible.
7. Fresh tumor biopsy at Screening is required if clinically feasible. If fresh tissue cannot be obtained, then archived tumor tissue from a recent biopsy (≤24 months old) must be provided.

**Table 1-9 Minimal Residual Disease CCI Evaluation Schedule – Subjects with RRMM – Expansion Part A (GEN3014 Single Cohorts)**

Screening or Treatment Cycle (28 days per cycle)	Screening	Post-treatment Collection
Day (window)	Day -21 to Day -1	±1 month
Bone marrow aspirate for MRD	X	At CR/sCR, and at 6, 12, 18, 24, and 30 months post C1D1 for subjects who achieve CR/sCR and remain on trial
Whole blood MRD CCI	X	At CR/sCR, and at 6, 12, 18, 24, and 30 months post C1D1 for subjects who achieve CR/sCR and remain on trial

C=cycle; D/d=day; CR=complete remission; CCI; MRD=minimal residual disease; RRMM=relapsed or refractory multiple myeloma; sCR=stringent complete response.

**Table 1-10 Minimal Residual Disease Evaluation Schedule – Subjects with R/R AML – Expansion Part A (GEN3014 Single Cohorts)**

Screening or Treatment Cycle (28 days per cycle)	Screening	Cycles 2, 3, 6, 9, and 12	Additional Post-treatment Collections
Day (window)	Day -21 to Day -1	Day 1 (±3d for C2, ±7d for C3; ±1 cycle for all others)	±1 month
Bone marrow aspirate for MRD	X	X	At CR/CRi, and at 6, 12, 18, 24, and 30 months post C1D1 for subjects who achieve CR/CRi and remain on trial.

C=cycle; D/d=day; CR=complete remission; CRi=complete remission with incomplete hematologic recovery; CCI; MRD=minimal residual disease; R/R AML=relapsed or refractory acute myeloid leukemia.

**Table 1-11 Minimal Residual Disease CCI Evaluation Schedule – Subjects with R/R DLBCL – Expansion Part A (GEN3014 Single Cohorts)**

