**Table 3-3 Objectives and Endpoints – Expansion Part B (Randomized H2H)**

Objectives	Endpoints
Primary	

 
Compare overall response of GEN3014 IV vs daratumumab SC in anti-CD38 mAb-naïve RRMM subjects
 
	
 
ORR
 

Secondary	

 
Compare PK between GEN3014 IV vs daratumumab SC
 
	
 
Ctrough levels of GEN3014 IV, or daratumumab SC, on Cycle 3 Day 1
 

 
Assess the anti-tumor activity of GEN3014 IV vs daratumumab SC
 
	
 
VGPR or better
 
CR or better
 
DOR
 
TTR
 
PFS
 
OS
 
Time to next therapy (TTNT)
 

 
Assess safety of GEN3014 IV vs daratumumab SC
 
	
 
Safety: Incidence and severity of AEs and SAEs, including changes in laboratory values, vital signs, ECGs
 
Immunogenicity: Anti-GEN3014 antibodies, anti-daratumumab antibodies
 

Exploratory	

 
Evaluate the pharmacodynamic profiles of GEN3014 and compare with those of daratumumab
 
	
 
Pharmacodynamic markers in blood and tumor samples, including frequencies of NK cells and other leukocyte subsets, and complement analyses
 

 
Assess potential biomarkers predictive of clinical response to GEN3014 and evaluate potential surrogacy with PFS and OS
 
	
 
CCI [REDACTED]
 
CCI [REDACTED]
 
CCI [REDACTED]
 

 
Assess MRD status
 
	
 
Rate and duration of MRD-negative remission
 

 
Explore PK/pharmacodynamic relationship (PK/anti-tumor activity) and PK/safety
 
	
 
Dose concentration response (biomarkers and/or efficacy, safety) relationship
 

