## 10.9 Appendix 9: 2016 International Myeloma Working Group (IMWG) Uniform Response Criteria for Response and Minimal Residual Disease Assessment in Multiple Myeloma

IMWG criteria for response assessment including criteria for MRD 	
Response Subcategory	Response Criteria
IMWG MRD criteria (requires a complete response as defined below)	
Sustained MRD-negative	MRD negativity in the marrow (NGF, NGS, or both) and by imaging as defined below, confirmed minimum of 1 year apart. Subsequent evaluations can be used to further specify the duration of negativity (eg, MRD-negative at 5 years) 
Flow MRD-negative	Absence of phenotypically aberrant clonal plasma cells by NGF  on bone marrow aspirates using the EuroFlow standard operation procedure for MRD detection in MM (or validated equivalent method) with a minimum sensitivity of 1 in 10  nucleated cells or higher
Sequencing MRD-negative	Absence of clonal plasma cells by NGS or bone marrow aspirate in which presence of a clone is defined as less than 2 identical sequencing reads obtained after DNA sequencing of bone marrow aspirates using the LymphoSIGHT platform (or validated equivalent method) with a minimum sensitivity of 1 in 10  nucleated cells  or higher
Imaging plus MRD-negative	MRD negativity as defined by NGF or NGS plus disappearance of every area of increased tracer uptake found at baseline or a preceding PET/CT or decrease to less mediastinal blood pool SUV or decrease to less than that of surrounding normal tissue 
Standard IMWG response criteria 	
sCR	Complete response as defined below plus normal FLC ratio  and absence of clonal cells in bone marrow biopsy by IHC ( $\kappa/\lambda$ ratio $\leq 4:1$ or $\geq 1:2$ for $\kappa$ and $\lambda$ patients, respectively, after counting $\geq 100$ plasma cells 
CR	Negative IFE on the serum and urine and disappearance of any soft tissue plasmacytomas and $\leq 5\%$ plasma cells in bone marrow aspirates
VGPR	Serum and urine M-protein detectable by IFE but not on electrophoresis or $\geq 90\%$ reduction in serum M-protein plus urine M-protein level $< 100$ mg per 24 h

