### **5.5.3      *Treatment Emergent Fatal AEs and Deaths***

The number and percentage of subjects who died due to related TEAE will be summarized by PT. All fatal adverse events will be presented in a separate listing, indicating relationship to treatment.

All deaths as reported on the eCRF death form will be summarized by primary cause of death. In addition, deaths occurring within 30 or 60 days of first GEN3014 dose, or within 30 or 60 days of last GEN3014 dose will be summarized by primary cause of death.

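### SAP 5.6.4 judges MRD on whole blood alone, which fixes the AML rate at 0/20 and ignores marrow results in RRMM and DLBCL; SAP 5.6.3 and 5.5.3 also need wording fixes for the daratumumab arm

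*SAP*

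**What the plan says.** **MRD rule.** SAP 5.6.4 defines MRD negativity as "no malignant clone sequence being detected at a given threshold in PBMCs or ctDNA". At subject level, "subjects are considered MRD negative if there is at least one on-treatment MRD negative whole blood sample". Everyone who does not meet this condition is counted as positive, and the SAP gives subjects who have no MRD assessment as an example. Marrow is not mentioned. The rate is analysed as ORR is, so with an exact Clopper-Pearson interval. Protocol 9.4.4.1 asks only for one MRD-negative sample and names no specimen. SAP 6.1 records no change from the protocol's analyses.

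**MRD specimens in the protocol.**
- AML: Table 1-10 has a single row, bone marrow aspirate, taken at Cycles 2, 3, 6, 9 and 12 and also "At CR/CRi, and at 6, 12, 18, 24, and 30 months post C1D1 for subjects who achieve CR/CRi and remain on trial". Section 8.2.2.2 likewise assigns part of the marrow aspirate to MRD.
- RRMM: Tables 1-4, 1-9 and 1-15 schedule both marrow aspirate and whole blood. Section 10.9 heads its MRD block "IMWG MRD criteria (requires a complete response as defined below" and defines flow and sequencing negativity on marrow aspirate at a sensitivity of at least 1 in 10^5.
- DLBCL: Table 1-11 schedules whole blood for all. Where marrow is involved, it requires an aspirate to confirm MRD negativity in CR.

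**Daratumumab-arm safety.** SAP 5.6.3 lists "any anti-drug antibodies to GEN3014 or rHuPH20 (for subjects treated with daratumumab SC in Expansion Part B". Current protocol Table 3-3 has "Immunogenicity: Anti-GEN3014 antibodies, anti-daratumumab antibodies" and no rHuPH20. SAP Table 3 lists all three analytes. SAP 5.5.3 summarises "deaths occurring within 30 or 60 days of first GEN3014 dose, or within 30 or 60 days of last GEN3014 dose".

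**The concern.** The rate and duration of MRD-negative remission in AML are named exploratory endpoints of Expansion Part A (protocol Table 3-2, SAP Table 2). A rule that can be met only by a specimen AML subjects are not scheduled to give fixes the rate before any data arrive and leaves no durations to analyse. In RRMM and DLBCL the same rule can misclassify subjects. The error would carry into MRD duration and into the optional PFS and OS analyses by MRD status.

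The ADA wording matters because anti-daratumumab antibodies are part of a secondary safety objective in the randomised comparison, yet the only SAP section that describes the ADA analysis names a different analyte for that arm. The death windows cannot be computed for subjects who never receive GEN3014.

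**Working it through.** The documents give no design figure for MRD or ADA, so there is nothing of the plan's own to reproduce. The check sets the SAP rules against the sampling schedules and works out the AML consequence.

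**1. AML expansion cohort**

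Inputs: N = 20 (SAP section 3); marrow is the only scheduled MRD specimen (protocol Table 1-10, Section 8.2.2.2); no whole-blood result means MRD positive (SAP 5.6.4).

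Number negative under the rule: 0 of 20. Exact upper 95% limit for 0/n = 1 − 0.025^(1/n) = 1 − 0.025^(1/20) = 16.8%. Reported result: 0% (95% CI 0 to 16.8%).

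If marrow counted, as protocol 9.4.4.1 allows, the same method would give the following. The counts are assumed, since the documents state no expected rate.

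| Marrow-negative | Rate | Exact 95% CI |
|---|---|---|
| 1/20 | 5% | 0.1 to 24.9% |
| 2/20 | 10% | 1.2 to 31.7% |
| 4/20 | 20% | 5.7 to 43.7% |
| 6/20 | 30% | 11.9 to 54.3% |

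The chance that at least one of 20 subjects is marrow-negative is 1 − (1 − p)^20:

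| Assumed true rate p | Chance of at least one | Does 0 to 16.8% contain p? |
|---|---|---|
| 5% | 64% | yes |
| 10% | 88% | yes |
| 20% | 98.8% | no |
| 30% | 99.9% | no |

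In every row the SAP reports 0%.

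**2. RRMM and DLBCL**

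| Blood | Marrow | SAP 5.6.4 | Marrow-based definition |
|---|---|---|---|
| negative | negative | negative | negative |
| negative | positive | negative | positive |
| positive | negative | positive | negative |
| none | negative | positive | negative |

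The last column follows Section 10.9 for RRMM. For DLBCL with marrow involvement in CR, Table 1-11 makes row two the relevant conflict, because marrow must confirm negativity. Rows three and four also depart from protocol 9.4.4.1, which accepts one negative sample of either kind. The documents give no blood–marrow discordance rate, so the size of the misclassification cannot be computed.

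**3. ADA in the daratumumab arm**

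- Serum: scheduled at Screening, C1D1, C1D22, Day 1 of even cycles and end of treatment (protocol Table 1-14).
- Assay target: antibodies to trial drug (protocol 8.9).
- Analysis set: the IAS includes this arm (SAP 4.8).
- Anti-rHuPH20: not collected, according to the stated reason for its removal from Table 3-3 in Amendment 5.
- Version: the SAP was written against Amendment 3; the protocol is now at Amendment 5.

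Section 5.6.3 as worded therefore asks for a result that will not exist and does not ask for one that can, in about 40 of about 80 randomised subjects.

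**4. Deaths**

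The 30/60-day windows are undefined for the same 40 or so subjects. The preceding sentence of SAP 5.5.3, which summarises all deaths by primary cause, carries no drug restriction.

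**The case against.** Four points have force.

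- A reader might infer that the SAP as a whole analyses specimens the protocol does not collect. That is not supported. Whole-blood MRD is scheduled in RRMM and DLBCL, and ADA serum is drawn in the daratumumab arm. Only AML MRD fits that description.
- A reader might infer that Part B immunogenicity will have no comparator data. The samples exist, the IAS covers the arm, and SAP Table 3 lists anti-daratumumab. An empty column follows only from a literal reading of one parenthesis in 5.6.3. It is an internal inconsistency, and for rHuPH20 also a version lag. Nor are comparator deaths lost: all deaths are summarised, and OS is a Part B endpoint.
- In RRMM, post-baseline blood MRD is scheduled only at CR/sCR and later in subjects who achieve it, so the schedule largely supplies the CR condition. What stands is that marrow results are unused.
- The start of protocol 8.8.3, the MRD methods section, is redacted, and exploratory PBMCs are drawn in all Part A cohorts (Table 1-8). A blood-based AML MRD assay could be described there. No visible text assigns blood to AML MRD, and Tables 1-6 and 1-10 and Section 8.2.2.2 all point to marrow.

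**Conclusion.** The concern holds in this form. SAP 5.6.4 fixes the AML expansion MRD-negative rate at 0/20 (95% CI 0 to 16.8%), assuming the planned 20 subjects and that the redacted part of protocol 8.8.3 does not add a blood specimen for AML. In RRMM and DLBCL the rate is not forced to zero, but scheduled marrow results are disregarded and marrow-positive, blood-negative subjects count as negative. This goes against the IMWG appendix and Table 1-11, and the restriction to blood is not in protocol 9.4.4.1; the size is unknown. SAP 5.6.3 names the wrong analyte for the daratumumab arm, and the death windows in 5.5.3 leave that arm out. Both are wording faults with the underlying data available. MRD is exploratory, ADA is secondary, the interim rules use response, and the primary ORR analysis is untouched. The SAP should be corrected before database lock.

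**What to change.** Amend the SAP:

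1. **5.6.4:** define MRD negativity by disease on the scheduled specimen.
   - AML: marrow aspirate.
   - RRMM: marrow aspirate at 10^-5 in subjects with CR/sCR, with blood reported separately.
   - DLBCL: whole blood, plus marrow where involved at baseline.

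   Counting subjects without data as not negative can stay once the specimen is right.
2. **5.6.3 and Table 3:** replace rHuPH20 by daratumumab in 5.6.3 and delete rHuPH20 from Table 3, so that both match current protocol Table 3-3.
3. **5.5.3:** anchor the 30/60-day windows to the first and last dose of trial drug.

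The cost is SAP wording and the matching programming. The samples are already scheduled, and no visit or assay is added.

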**Table 1-15 Minimal Residual Disease CCI Evaluation Schedule – Subjects with RRMM – Expansion Part B (Randomized H2H)**

Screening or Treatment Cycle (28 days per cycle)	Screening	Post-treatment Collection
Day (window)	Day -21 to Day -1	±1 month
Bone marrow aspirate for MRD	X	At CR/sCR, and at 6, 12, 18, 24, and 30 months post C1D1 for subjects who achieve CR/sCR and remain on trial
Whole blood MRD CCI	X	At CR/sCR, and at 6, 12, 18, 24, and 30 months post C1D1 for subjects who achieve CR/sCR and remain on trial

C=cycle; CR=complete remission; CCI; D/d=day; H2H=head-to-head; MRD=minimal residual disease; RRMM=relapsed or refractory multiple myeloma; sCR=stringent complete response.

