### **9.4.4 Exploratory Analysis**

#### ***9.4.4.1 Rate and Duration of MRD-Negative Remission***

The rate of MRD-negative remission is defined as the proportion of subjects with at least 1 MRD-negative sample. MRD-negative remission applies to RRMM in both the Dose Escalation and the Expansion, but only applies to R/R AML and R/R DLBCL in the Expansion.

Duration of MRD-negative remission is defined as the number of days from the date of the first documented MRD-negative sample to the date of MRD status change (not MRD-negative). This will be censored and analyzed using the same statistical methodology as for PFS.

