Relapse from CR  (To be used only if the endpoint studied is disease-free survival)	
Any 1 or more of the following:
 
 
Reappearance of serum or urine M-protein by IFE or electrophoresis;
 
Development of <math>\geq 5\%</math> plasma cells in the bone marrow;
 
Appearance of any other sign of progression (ie, new plasmacytoma, lytic bone lesion, or hypercalcemia)
 

Relapse from MRD negative  (To be used only if the endpoint is disease-free survival)	
Any 1 or more of the following:
 
 
Loss of MRD-negative state (evidence of clonal plasma cells on NGF or NGS, or positive imaging study for recurrence of myeloma);
 
Reappearance of serum or urine M-protein by IFE or electrophoresis;
 
Development of <math>\geq 5\%</math> plasma cells in the bone marrow;
 
Appearance of any other sign of progression (ie, new plasmacytoma, lytic bone lesion, or hypercalcemia)
 

CR=complete response; CRAB=calcium elevation, renal failure, anaemia, lytic bone lesions; DFS=disease-free survival; CT=computed tomography; FCM=flow cytometry; FDG=fluorodeoxyglucose; FLC=free light chain; h=hour(s); IFE=immunofixation; IHC=immunohistochemistry; mAb=monoclonal antibody; MM=multiple myeloma; MR=minimal response; MRD=minimal residual disease; NGF=next generation flow; NGS=next generation sequencing; MFC=multiparameter flow cytometry; PD=progressive disease; PET=positron emission tomography; PFS=progression-free survival; PR=partial response; sCR=stringent complete response; SD=stable disease; SPD=sum of the product of the maximal perpendicular diameters of measured lesions; SUV=standardized uptake value; SUVmax=maximum standardized uptake value; VGPR=very good partial response.

For MRD assessment, the first bone marrow aspirate should be sent to MRD (not for morphology) and this sample should be taken in 1 draw with a volume of minimally 2 mL (to obtain sufficient cells), but maximally 4 to 5 mL to avoid hemodilution.

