### 5.4.3 DOR

Duration of response (DOR, months) is defined as time from date of first documented initial response (PR or better) to date of progression, or death, whatever comes first. As such, DOR is defined only for the subjects (in the analysis set) who achieve PR or better. DOR will be censored following the censoring scheme for time to event variables as presented in [Table 8](#).

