**Table 8: Censoring scheme for time to event variables**

Situation	Date of Progression or Censoring	Censoring Rule
Incomplete or no baseline assessments	C1D1, or date of randomization	Censored
No documented PD or death prior to analysis data cutoff, trial discontinuation, start of new anti-cancer treatment	Date of last valid tumor assessment with no documented PD before the situation*	Censored
Documented PD between adequate** assessment visits	First date of assessment demonstrating documented PD	Event
Death before first response assessment	Date of death	Event
Death between adequate** assessment visits	Date of death	Event
Death or documented PD after two or more consecutive missed visits***	Date of last valid tumor assessment prior to the missed visits*	Censored

\*Excluding response assessments with NE as overall time point response. If no such assessment exists, the censoring date will be C1D1.

\*\* No more than one missed visit, no anti-cancer therapy etc. before the death or documented progression.

\*\*\* Please refer to the DPS for the definition of two missed scans.

Clinical progression (as recorded in eCRF) does not constitute documented progression and will cause censoring (unless documented progression was recorded before clinical progression).

DOR will be estimated using the KM method and the result will be displayed graphically. The number and percentage of subjects with event or censoring will be reported. Median DOR (months) with associated 95% CI as well as first and third quartiles and range will be provided.

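### Duration of MRD negativity ends only at an MRD status change, which does not agree with the DOR/PFS method it refers to, so the handling of progression and death is left open

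*SAP*

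**What the plan says.** **End event.** The SAP gives it in 5.6.4: "Duration of MRD negativity is defined as the number of days from the first documentation of MRD- to the date of MRD status change". Protocol 9.4.4.1 counts from the first MRD-negative sample "to the date of MRD status change (not MRD-negative". Neither sentence mentions progression or death.

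**Method.** SAP 5.6.4 adds that "duration of MRD- analyses will be conducted in similar methods for DOR". The protocol says: "This will be censored and analyzed using the same statistical methodology as for PFS". SAP 5.4.3 defines DOR as "time from date of first documented initial response (PR or better) to date of progression, or death, whatever comes first", and PFS likewise ends at PD or death. SAP Table 8 makes "Documented PD between adequate assessment visits" an event and treats death between adequate visits the same way. It has no row for an MRD result.

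**Sampling in myeloma.** Tables 1-9 and 1-15 schedule MRD samples at screening, at CR/sCR, and at five later time points ending at "30 months post C1D1 for subjects who achieve CR/sCR and remain on trial". Neither table has a collection at progression or End of Treatment. Footnote 12 of Tables 1-5 and 1-12 adds a marrow aspirate at End of Treatment/PD in Parts A and B, only if clinically feasible.

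**Status.** Duration of MRD-negative remission is an exploratory endpoint in Part A (Table 3-2) and Part B (Table 3-3). In Dose Escalation only the rate is listed.

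**The concern.** The definition and the method it refers to give different answers for the same subject. Take a myeloma subject who is MRD-negative at month 6 and progresses at month 10. Under the definition there has been no MRD status change, so the subject is censored. Under the DOR/PFS rules the subject has an event at month 10. Two programmers could each follow the SAP and draw different Kaplan-Meier curves.

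The literal reading is the harmful one. A subject who progresses or dies has lost the remission being timed, or can no longer be in it. Censoring that subject assumes that the remission would have continued as in those still under observation. The censoring is therefore informative, and the estimated duration is too long. Part B sets the two arms side by side, and the distortion need not be equal in both.

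**Working it through.** The plan states no figure for this endpoint, so there is nothing to reproduce. The check is first textual; the sizes that follow are illustrations.

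**1. Does the reference to DOR bring in its event list?** Compare the endpoints that share the method:

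| Endpoint | Place | Events named |
|---|---|---|
| DOR | SAP 5.4.3 | Progression, death |
| PFS | SAP 5.4.5 | PD, death from any cause |
| TTNT | SAP 5.4.7 | Next anti-cancer therapy, death due to PD |
| MRD-negative duration | SAP 5.6.4, protocol 9.4.4.1 | MRD status change |

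TTNT is also to be analysed by methods similar to DOR, yet it has its own event list and censors deaths from other causes. So in this SAP a reference to the DOR method does not by itself carry over the DOR events. For TTNT the differing rules are written out; for MRD duration they are not. Table 8 also censors at the last valid tumor assessment and has a rule for two missed visits, and neither is defined for a roughly 6-monthly MRD schedule.

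**2. Is progression without a documented MRD change likely?** In myeloma, yes.
- Samples after CR are about 6 months apart.
- Marrow tests at CR/sCR and beyond are required only if blood and urine show near CR or better, which a progressing subject would usually not meet.
- Disease assessments are not required once PD is confirmed.
- The optional End of Treatment/PD aspirate appears in Tables 1-8, 1-13 and 1-14 under immunophenotyping and sequencing, while SAP 5.6.4 judges MRD status for the rate on whole blood.
- A subject who dies between samples cannot show a change at all.

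Sampling is denser in AML (Cycles 2, 3, 6, 9 and 12, plus CR-based time points; Table 1-10) and, early on, in DLBCL (Cycles 1, 3, 5, 7 and 10, then every 6 months; Table 1-11). The myeloma sizes below should not be carried over to them.

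**3. Size, closed form (assumed rates).** Let λ1 be the constant hazard of a documented MRD change and λ2 = r·λ1 the hazard of PD or death without one.
- Median with PD/death censored: ln 2 / λ1.
- Median with PD/death as events: ln 2 / (λ1 + λ2).
- Ratio of the two: 1 + r.

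With ln 2 / λ1 = 18 months:
- r = 0.25: 18 against 18/1.25 = 14.4 months.
- r = 0.5: 18 against 18/1.5 = 12.0 months.
- r = 1: 18 against 18/2 = 9.0 months.

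**4. Size, simulation on the myeloma schedule (assumed rates).** There were 20,000 subjects per scenario. The first negative sample is at month 6, with further samples at months 12, 18, 24 and 30 that stop at PD. Time to MRD loss is exponential, and PD follows after an exponential lag. Deaths are not modelled separately. The estimates are Kaplan-Meier at 18 months after the first negative sample.

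| Median to MRD loss (months) | Median lag to PD (months) | PD before a documented change | PD censored | PD as event | Difference |
|---|---|---|---|---|---|
| 9 | 3 | 41% | 0.45 | 0.25 | 0.20 |
| 9 | 6 | 25% | 0.36 | 0.25 | 0.11 |
| 9 | 12 | 14% | 0.30 | 0.25 | 0.05 |
| 12 | 3 | 36% | 0.55 | 0.35 | 0.20 |
| 12 | 6 | 22% | 0.46 | 0.35 | 0.11 |
| 12 | 12 | 12% | 0.41 | 0.35 | 0.06 |
| 18 | 3 | 28% | 0.68 | 0.50 | 0.18 |
| 18 | 6 | 17% | 0.60 | 0.50 | 0.10 |
| 18 | 12 | 10% | 0.56 | 0.50 | 0.06 |

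The PD-censored column censors at the last MRD sample; censoring at the PD date changes it by at most 0.01. The rows with a 12-month median also show the risk for an arm comparison. Two arms with the same MRD loss but lags of 3 and 12 months would read 0.55 and 0.41 with PD censored, and 0.35 in both with PD counted.

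**The case against.** The strongest reply is that the documents never say that progression and death are censored. Both sections refer to methods in which they are events, and no row of Table 8 censors an adequately documented PD or a death between adequate visits. Applied that way, the overstatement is zero. This stands as a possible reading, and it rules out the claim that the plan builds in a bias. It does not remove the conflict, because the stated end event is still an MRD change alone and the TTNT section shows that the DOR reference does not fix the events.

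A reader might also infer that MRD sampling stops at progression. No passage says so. Samples are for subjects who remain on trial, protocol 7.1 keeps subjects in the trial after they stop drug, and an aspirate may be taken at End of Treatment/PD. What can be said is that no MRD sample is scheduled at progression.

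It is tempting to cite protocol Appendix 9, whose entry for relapse from MRD negativity includes "Appearance of any other sign of progression (ie, new plasmacytoma, lytic bone lesion, or hypercalcemia". That entry is restricted to disease-free survival, and note 11 of the appendix repeats the limit. Disease-free survival is not an endpoint here, so the entry shows no contradiction.

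Finally, the SAP leaves programming detail to a data presentation specification that is not among the documents, and protocol 8.8.3 is partly redacted. A rule may exist there, but an end event belongs in the endpoint definition.

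**Conclusion.** The definition and the method it refers to do not agree, and the plan does not settle whether PD or death without a documented MRD change is an event. If the definition is followed literally, the duration is overstated; if Table 8 is applied, it is not. It would go too far to conclude that the plan censors competing events and will overstate the duration.

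No size can be derived from the documents, which give no rates. In the illustration, with a median time to MRD loss of 9 to 18 months and a median lag to PD of 3 to 12 months on the myeloma schedule, the literal reading adds about 5 to 20 percentage points at 18 months. The other reading adds nothing.

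Importance is low: the endpoint is exploratory, the trial has no predefined hypotheses, and no planned decision rests on this duration.

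**What to change.** In SAP 5.6.4 and protocol 9.4.4.1, define the end of MRD-negative duration as the first of:
- an MRD-positive result;
- documented PD (relapse for AML);
- death from any cause.

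Otherwise, censor at the last MRD-negative assessment. Add a matching MRD row to SAP Table 8, so that the censoring date refers to MRD assessments and not tumor assessments.

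If time to MRD conversion alone is also of interest, report its cumulative incidence with PD and death as competing events.

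The cost is one sentence in each document and one table row, before database lock. No new data or samples are needed.
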